# 6.3.3 Other Immunogenicity Exploratory Endpoints

The below exploratory analyses of immunogenicity may be performed for the Cohort A and Cohort B substudies separately:

GM level (as described in Section 6.3.2) and GMFR (compared to Day 1) to vaccine mismatched strains at all evaluable time points,

Frequency, specificities, or other endpoints to be determined for the further characterization of immune responses.

# 6.4 Multiplicity Control

No multiplicity adjustment will be needed between the Cohort A and B substudies.

For Cohort A, a 2-sided alpha of 0.05 will be fully spent as shown in the testing sequence for coprimary and secondary endpoints in Figure 2 and described below:

Step 1 (Noninferiority): Test null hypotheses  $\underline{H^1_0}$  and  $\underline{H^2_0}$ , each at a 2-sided 0.025 level.

If both null hypotheses  $\underline{H^1_0}$  and  $\underline{H^2_0}$  in Step 1 are rejected, then proceed to Step 2 below using  $\alpha_1$ =5% level.

If only null hypotheses  $\underline{H^1_0}$  is rejected, then proceed to Step 2 below using  $\alpha_1$ =2.5% level.

Step 2 (Superiority GM level for 4 Influenza strains): Test null hypotheses  $\underline{H^3}_0$  at the  $\alpha_1$  two-sided level.

If null hypotheses  $\underline{H}_{0}^{3}$  rejected, then proceed to Step 3 below:

Step 3 (Superiority GM level for 1 SARS-CoV-2 strain): Test null hypotheses  $\underline{H^4}_0$  at the  $\alpha_1$  two-sided level.

If null hypotheses  $\underline{H_0}$  rejected, and  $\underline{H_0}$  rejected in Step 1, then proceed to Step 4 below.

 $\underline{\text{Step 4 (Superiority SCR for 4 Influenza strains)}}\text{: Test null hypotheses }\underline{\text{H}^5_0}\text{ at a 2-sided 0.05 level.}$ 

If null hypotheses  $\underline{H}_{0}^{5}$  rejected, then proceed to Step 5 below:

Step 5 (Superiority SRR for 1 SARS-CoV-2 strain): Test null hypotheses  $\underline{H^6_0}$  at a 2-sided 0.05 level.

In the event that neither  $\underline{H^1_0}$  nor  $\underline{H^2_0}$  is rejected, then the testing sequence will stop, and all steps thereafter will not be conducted. Detailed descriptions are presented in Section 4.2 of this SAP.

All other endpoints are not controlled for multiplicity and the analyses are descriptive in nature.

Similarly for Cohort B, a 2-sided alpha of 0.05 will be fully spent, as shown in the testing sequence for coprimary and secondary endpoints in Figure 2 and described below:

Step 1 (Noninferiority): Test null hypotheses  $\underline{H^1_0}$  and  $\underline{H^2_0}$ , each at a 2-sided 0.025 level.

If both null hypotheses  $\underline{H^1_0}$  and  $\underline{H^2_0}$  in Step 1 are rejected, then proceed to Step 2 below using  $\alpha_1$ =5% level.

If only null hypotheses  $\underline{H^1_0}$  is rejected, then proceed to Step 2 below using  $\alpha_1$ =2.5% level. Step 2 (Superiority GM level for 4 Influenza strains): Test null hypotheses  $\underline{H^3_0}$  at the  $\alpha_1$  two-sided level.

If null hypotheses  $\underline{H_{0}}$  rejected, then proceed to Step 3 below:

Step 3 (Superiority GM level for 1 SARS-CoV-2 strain): Test null hypotheses  $\underline{H^4_0}$  at the  $\alpha_1$  two-sided level.

If null hypotheses  $\underline{H^4}_0$  rejected, and  $\underline{H^2}_0$  rejected in Step 1, then proceed to Step 4 below.

Step 4 (Superiority SCR for 4 Influenza strains): Test null hypotheses  $\underline{H_0}$  at a 2-sided 0.05 level.

[figure not shown]
If null hypotheses  $\underline{H}_{0}^{5}$  rejected, then proceed to Step 5 below:

Step 5 (Superiority SRR for 1 SARS-CoV-2 strain): Test null hypotheses  $\underline{H^6_0}$  at a 2-sided 0.05 level.

In the event that neither  $\underline{H^1_0}$  nor  $\underline{H^2_0}$  is rejected, then the testing sequence will stop, and all steps thereafter will not be conducted. Detailed descriptions are presented in Section 4.2 of this SAP.

All other endpoints are not controlled for multiplicity and the analyses are descriptive in nature.

Figure 2 Hypotheses testing sequence for coprimary and secondary endpoints

Abbreviations: CI = confidence interval; GM = geometric mean; H = Hypothesis; SCR = seroconversion rate, SRR = seroresponse rate.

# 6.5 Safety Analyses

Safety and reactogenicity will be assessed by clinical review of all relevant parameters, including solicited ARs (local and systemic events), unsolicited AEs, SAEs, AESIs, MAAEs, severe AEs, and AEs leading to withdrawal from study participation.

All safety analyses will be provided for the Cohort A and Cohort B substudies separately.

Participants will be included in the treatment arm corresponding to what they actually received and will be based on the Safety Set, except summaries of solicited ARs, which will be based on the Solicited Safety Set, unless otherwise specified. When summarizing the number and percentage of participants with an event, participants will be presented according to the highest severity/toxicity in the summaries by severity/toxicity. Imputation rules for missing/partial dates is detailed in Appendix E.

An additional pooled safety analysis that combines the mRNA-1083 + placebo arm from the two cohorts may also be carried out. Summaries of local solicited ARs and AEs may also be presented by vaccination group and injection content received in the corresponding side/deltoid.

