4.2. Scientific Rationale for Study Design

This study is designed to show noninferior immunogenicity of mRNA-1083 as compared with Fluarix and Spikevax in healthy adults 50 to <65 years of age or Fluzone HD and Spikevax in healthy adults 65 years of age or greater.

In this observer-blind study, participants, clinic staff involved in participant assessment, and Sponsor personnel (or its designees) will be blinded to participant vaccine allocation. A limited number of Sponsor and/or CRO personnel will be unblinded to conduct safety data analyses for the DSMB safety data reviews (as described in the DSMB charter) and perform the primary analysis. Unblinded study personnel, who will not participate in any other aspect of the study, will perform study intervention accountability, dose preparation, and study intervention administration.

The NP swab specimen(s) for assessment of pathogens, including influenza virus and SARS-CoV-2, will be collected prior to study injection on Day 1 (see Section 8.3.4).

[figure not shown]

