9.5.3. Safety Analyses

The safety analyses will be separately performed by Cohort A and B, respectively.

All safety analyses will be based on the Safety Set of each cohort, except summaries of solicited ARs, which will be based on the Solicited Safety Set of each cohort. All safety analyses will be provided by treatment group. Participants will be included in the treatment group corresponding to what they actually received.

Safety and reactogenicity will be assessed by clinical review of all relevant parameters, including solicited ARs (local and systemic events), unsolicited AEs, SAEs, AESIs, MAAEs, severe AEs, and AEs leading to withdrawal from study participation.

The number and percentage of participants with any solicited local AR, solicited systemic AR, and solicited AR during the 7-day postinjection follow-up will be summarized. A two-sided 95% exact CI using the Clopper-Pearson method will also be provided for the percentage of participants with any solicited AR. Solicited ARs and grades are defined in Section 10.5.

The number and percentage of participants with unsolicited AEs, SAEs, AESIs, MAAEs, severe AEs, and AEs leading to withdrawal from study participation will be summarized. Unsolicited AEs will be coded according to MedDRA and presented by MedDRA system organ class and preferred term.

Solicited ARs will be coded according to the MedDRA for AR terminology. The Toxicity Grading Scale for Healthy Adult and Adolescent Volunteers Enrolled in Preventive Vaccine Clinical Trials (DHHS 2007) will be used in this clinical study.

The number of events of unsolicited AEs, SAEs, AESIs, MAAEs, severe AEs, and AEs leading to withdrawal from study participation will be reported in summarization tables accordingly.

The analysis strategy for safety parameters is presented in Table 10. For all other safety parameters, descriptive summary statistics will be provided. Further details will be described in the SAP.

Table 10: Analysis Strategy for Safety Parameters

Safety Endpoint	Number and Percentage of Participants	Number of Events	95% CI
Any solicited AR (overall and by local, systemic)	✓	NA	✓
Any unsolicited AE	✓	✓	NA
Any unsolicited treatment-related AE	✓	✓	NA
Any SAE	✓	✓	NA
Any treatment-related SAE	✓	✓	NA
Any unsolicited AESI	✓	✓	NA
Any unsolicited treatment-related AESI	✓	✓	NA
Any unsolicited MAAE	✓	✓	NA
Any unsolicited treatment-related MAAE	✓	✓	NA
Any unsolicited severe AE	✓	✓	NA
Any unsolicited treatment-related severe AE	✓	✓	NA

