#### 4 STUDY DESIGN

## 4.1 Overall Study Design

This study will be a Phase 3, randomized, stratified, observer-blind, active-control study conducted in 2 age-group substudies (Cohort A and Cohort B). This clinical study consists of 2 separate substudies:

[figure not shown]
Cohort A will evaluate the safety, reactogenicity, and immunogenicity of the 40 µg mRNA 1083 vaccine and dose level as compared with co administered active licensed comparator vaccines (Fluzone® HD and Spikevax) in healthy adults ≥65 years of age.

Cohort B will evaluate the safety, reactogenicity, and immunogenicity of the 40  $\mu$ g mRNA 1083 vaccine and dose level as compared with co administered active licensed comparator vaccines (Fluarix® and Spikevax) in healthy adults 50 to <65 years of age.

Each of the 2 independent substudies has its own separate hypotheses and statistical analyses, and its own multiplicity control for overall Type I error rate (2-sided alpha of 5%) for the co-primary endpoints within the substudy.

Overall, the study will enroll approximately 8000 participants with approximately 4000 participants (in a 1:1 ratio) in Cohort A and approximately 4000 participants (in a 1:1 ratio) in Cohort B. The study schema is presented in Figure 1.

Figure 1 Study Schematic and Participant Disposition

On Day 1, each participant will receive 2 injections administered IM, 1 in each deltoid. The interventions administrated are described in Table 1.

Table 1 Study Arms and Interventions Administered

Substudies	Arm Titles	Arm Types	Arm Descriptions
Cohort A (≥65 years of age)	mRNA 1083 + Placebo n=2000	Experimental	Participants will receive mRNA 1083 (40 µg) and Placebo, administered as IM injections, 1 in each deltoid muscle on Day 1.
Sı	Fluzone HD + Spikevax n=2000	Active Comparator	Participants will receive Fluzone HD and Spikevax administered as IM injections, 1 in each deltoid muscle on Day 1.
Cohort B (50 to <65 years of age)	mRNA-1083 + Placebo n=2000	Experimental	Participants will receive mRNA-1083 (40 µg) and Placebo, administered as IM injections, 1 in each deltoid muscle on Day 1.
n=4000	Fluarix + Spikevax n=2000	Active Comparator	Participants will receive Fluarix and Spikevax, administered as IM injections, 1 in each deltoid muscle on Day 1.

Study details include:

Study duration: approximately 6 months, including the Screening period.

Treatment duration: Study injections are scheduled for all participants on Day 1 (Baseline).

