## 4.3 Sample Size and Power

With approximately 2000 participants in Cohort A and 2000 participants in Cohort B (a total of 4000) exposed to study vaccine in the mRNA-1083 (40  $\mu$ g) + Placebo group, this study will have approximately over 95% probability to observe at least 1 participant with an AE given a true 0.1% AE rate.

A subset of participants will be randomly selected from the FAS of Cohort A and B, respectively, to be tested by microneutralization assay according to the secondary objective.

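### The optional cross-cohort safety pool in SAP 6.5 takes in only the mRNA-1083 arms, so no combined randomised contrast is prespecified for rare events

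*SAP*

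**What the plan says.** Both documents plan safety by cohort. Protocol 9.5.3 states: "The safety analyses will be separately performed by Cohort A and B, respectively". SAP 6.5 agrees: "All safety analyses will be provided for the Cohort A and Cohort B substudies separately". Within a cohort the arms appear side by side, since Protocol 9.5.3 also states: "All safety analyses will be provided by treatment group". SAP 6.5.2.1 and 6.5.2.2 carry this through to SAEs, AESIs, MAAEs, severe events and events leading to discontinuation.

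SAP 6.5 then foresees one safety analysis that crosses the cohorts: "An additional pooled safety analysis that combines the mRNA-1083 + placebo arm from the two cohorts may also be carried out". It is optional and names only the mRNA-1083 + Placebo arms. Protocol 9.5.3 mentions no pooling. The other cross-cohort analysis, SAP 6.3.2.3, concerns immunogenicity and is likewise confined to the mRNA-1083 arms. Neither document plans a pooled or cohort-stratified safety comparison with the comparator arms.

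The rare-event justification in SAP 4.3 (also in Protocol 9.3) is nevertheless built on the two cohorts together. It starts from "With approximately 2000 participants in Cohort A and 2000 participants in Cohort B (a total of 4000) exposed to study vaccine" in the mRNA-1083 group and claims "approximately over 95% probability to observe at least 1 participant with an AE given a true 0.1% AE rate".

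**The concern.** Pooling across cohorts is most useful for SAEs, AESIs, deaths and the SMQ groups, where one cohort of 2000 per arm gives few events. Many of the listed AESIs (arrhythmia, myocardial infarction, stroke, thrombosis) also occur without vaccination in people aged 50 and over. A count from 4000 mRNA-1083 recipients therefore needs a comparator count beside it.

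The randomised comparators are available on the same schedule of activities, but the pool as worded leaves them out. Anyone wanting a combined contrast would have to build it from the two sets of cohort tables. If an imbalance prompted that after unblinding, the choice of events and method would not have been fixed in advance.

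**Working it through.** **Inputs from the documents**
- Exposed to mRNA-1083: 2000 per cohort, 4000 in all (SAP 4.3).
- Allocation: "approximately 4000 participants (in a 1:1 ratio) in Cohort A and approximately 4000 participants (in a 1:1 ratio) in Cohort B" (SAP 4.1), so about 2 × 2000 = 4000 comparator participants.
- Rare-event rate: 0.1% (SAP 4.3).

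**Step 1. Reproduce the plan's figure.** P(at least one event) = 1 − (1 − p)^n with p = 0.001.
- n = 4000: 1 − 0.999^4000 = 98.2%.
- n = 2000: 1 − 0.999^2000 = 86.5%.
- n = 3400 (4000 less 15%, borrowing the immunogenicity drop-out rate): 96.7%.

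The claim of over 95% is correct for the combined 4000 but is not met by one cohort. About 2995 exposed are needed, since ln(0.05)/ln(0.999) = 2994.2.

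**Step 2. Precision of the contrast.** At 0.1% in each arm, the 95% CI half-width for a risk difference is about 1.96 × √(2 × 0.001 × 0.999 / n).
- n = 2000 per arm: 0.00196, or 0.20 percentage points.
- n = 4000 per arm: 0.00139, or 0.14 percentage points.

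**Step 3. Illustrative power.** The documents give no comparator event rates, so the rates below are assumptions, taken as equal in both cohorts. Power is exact for a two-sided Fisher test at 5%, counting only an excess on mRNA-1083. Each cohort is 2000 v 2000 and the pool is 4000 v 4000, without stratification. Both cohorts' tables will be produced, so the table also shows the chance that at least one cohort reaches 5%, which is 1 − (1 − power)².

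| Assumed rates | One given cohort | At least one of two | Both arms pooled |
|---|---|---|---|
| 0.4% v 0.1% | 36% | 1 − 0.639² = 59% | 73% |
| 0.5% v 0.2% | 27% | 1 − 0.730² = 47% | 56% |
| 0.2% v 0.1% | 4.5% | 1 − 0.955² = 9% | 13% |

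Against what a reader of both cohorts' tables would already see, the gain is about 14 points in the first row, 10 in the second (46.7% to 56.3%) and 4 or 5 in the third.

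**Step 4. One concrete pattern.** A split of 8 v 2 in a cohort of 2000 per arm gives Fisher p = 0.11. The same split in both cohorts, 16 v 4 of 4000 per arm, gives p = 0.012.

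**The case against.** The strongest reply is that the safety evidence is already comparative. Each cohort's tables are by arm, and the objective of evaluating safety across arms is stated separately for each cohort, so those tables meet it. A stratified risk difference needs only the event counts and arm sizes that they contain. The cohorts are designed as independent substudies with different influenza comparators, as Protocol 4.2 shows: "noninferior immunogenicity of mRNA-1083 as compared with Fluarix and Spikevax in healthy adults 50 to <65 years of age or Fluzone HD and Spikevax" in the older group. The pool is optional, and a single-arm pool fits a single-arm exposure statement. Safety is judged by clinical review with no planned between-arm test, so power at the 5% level is only a rough gauge. An unblinded DSMB also reviews related SAEs; its charter is not in the documents, so whether it looks across cohorts is unknown.

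Most of this stands, and it limits the point. A reader might infer that the trial cannot separate an excess from background, or that the pooled rate has no reference at all. The documents do not support either reading, because comparator rates are reported within both cohorts. Nor is a rise from 36% to 73% the right measure of what is lost, since both cohorts' tables will be seen and the fair starting point is 59%.

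The reply does not remove the gap. That a contrast could be derived from published counts does not prespecify it, and the exposure statement says only that an event is likely to be seen, not whether it is in excess. Different influenza comparators argue against crude pooling but not against a cohort-stratified estimate.

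**Conclusion.** The point holds as a gap in prespecification. The one cross-cohort safety analysis that the SAP foresees is optional and single-arm, while the rare-event rationale depends on the combined 4000 (98.2% against 86.5% for one cohort). No combined randomised contrast is planned.

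The size is modest. Including the comparators narrows the risk-difference interval at 0.1% per arm by about 0.06 percentage points in half-width. For large relative increases it adds roughly 10 to 14 points of power over reading the two cohorts' tables side by side. It does not make the trial well powered for rare events: a doubling from 0.1% has about 13% power even when pooled. The power figures rest on assumed rates common to both cohorts and on an unstratified Fisher test, and serve only as illustration. No endpoint, hypothesis or primary table is affected.

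**What to change.** Reword the sentence in SAP 6.5 so that the pooled analysis, if run, combines both cohorts and shows both arms: mRNA-1083 + Placebo against licensed influenza vaccine (Fluzone HD or Fluarix) + Spikevax. For SAEs, AESIs, MAAEs, deaths and the SMQ groups, give the cohort-stratified Mantel-Haenszel risk difference with its 95% CI. Label it descriptive and keep the per-cohort tables as primary.

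The cost is one SAP sentence and a few table columns, from data already collected and coded; alpha is untouched. The small downside is that the influenza comparator differs by cohort, so the estimate is against a mixed licensed-vaccine control. Stratification respects this because every contrast stays within a cohort, and a footnote to the table should say so.

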#### **6.5.1** Solicited Adverse Reactions

Solicited ARs are a subset of AEs consisting of selected signs and symptoms that participants are asked to record/report. In this study, the solicited ARs are reactogenicity events. The eDiary will solicit daily participant reporting of ARs using a structured checklist. Participants will record such occurrences in the eDiary on the day of study injection (Day 1) and the 6 subsequent days, for a total of 7 days (through Day 7). Local ARs are expected after IM study injection. These are typically mild, transient, and self-limited and may include pain, erythema (redness),

swelling/induration (hardness) at the injection site and/or ipsilateral underarm swelling/tenderness. Systemic ARs may also occur after study injection, the majority of which are of mild to moderate in severity. Systemic ARs reported with other mRNA vaccines may include fatigue, headache, myalgia, fever, chills, arthralgia, vomiting, and/or nausea.

The term "reactogenicity" refers to the occurrence of transient adverse effects associated with vaccine administration. Severity grading of reactogenicity will occur automatically based on participant entry into the eDiary according to the grading scales presented in Appendix F modified from the Toxicity Grading Scale for Healthy Adult and Adolescent Volunteers Enrolled in Preventive Vaccine Clinical Trials (DHHS, 2007). All solicited ARs (local and systemic) will be considered causally related to dosing.

Any solicited AR that meets any of the following criteria must be entered into the participant's source document and must also be recorded in the participant's Reactogenicity eCRF:

Solicited local or systemic AR that results in a visit to an HCP (MAAE)

Solicited local or systemic AR leading to the participant withdrawing from the clinical study or the participant being withdrawn from the clinical study by the Investigator (AE leading to withdrawal).

Solicited local or systemic AR lasting beyond 7 days postinjection.

Solicited local or systemic AR that otherwise meets the definition of an SAE.

### Additionally:

If a participant reported a solicited AR during the solicited period and did not record the event in the eDiary, the event should be recorded on the Reactogenicity page of the eCRF.

If the event starts during the solicited period, but continues beyond 7 days after dosing, the participant should notify the site to provide an end date to close out the event on the Reactogenicity page of the eCRF.

If the participant reported an event after the solicited period (ie, after Day 7), it should be recorded as an AE on the AE page of the eCRF.

#### 6.5.1.1 Overview of Solicited ARs

An overall summary of solicited ARs up to 7 days after injection (with a toxicity grade of Grade 1 or greater) including the number and percentage of participants, by treatment arm (as defined in Section 6.1) will be presented. The number and percentage of participants experiencing any solicited local ARs and solicited systemic ARs of Grade 3 or higher will be provided as well.

#### 6.5.1.2 Solicited ARs by Toxicity Grade

A summary of solicited ARs up to 7 days after injection (with a toxicity grade of Grade 1 or greater) by toxicity grade, including the number and percentage of participants, by treatment arm (as defined in Section 6.1) who experience the following will be presented:

Any solicited ARs,

Any solicited systemic AR,

Any solicited local AR,

Each individual solicited systemic and local AR,

A 2-sided 95% exact CI using the Clopper-Pearson method will also be provided for the percentage of participants with any solicited AR (overall, local, and systemic). An additional description for Grade 3 or Above (Grade >=3) will be provided for all above categories. Summaries of local solicited ARs will be presented by vaccination group and injection content received in the corresponding side/deltoid. A summary figure will be produced for local and systemic event rates by toxicity grade.

# 6.5.1.3 Solicited ARs by Onset Day

A summary of solicited ARs up to 7 days after study injection (with a toxicity grade of Grade 1 or greater) by onset day (from Day 1 through Day 7), including the number and percentage of participants, by treatment arm (as defined in Section 6.1) who experience the following will be presented:

Any solicited ARs,

Any solicited systemic AR,

Any solicited local AR,

Each individual solicited systemic and local AR,

The onset of individual solicited AR is defined as the time point after injection (Section 6.1) at which the respective solicited AR first occurred. Summaries of local solicited ARs will be presented by vaccination group and injection content received in the corresponding side/deltoid.

